## **3.4        Protocol deviations**

Important protocol deviations are deviations from the protocol which potentially could have a meaningful impact on the evaluation of safety and efficacy outcome. Protocol deviations will be identified during ongoing data monitoring and cleaning process and will be reviewed in the Data Cleaning Meetings. The impact of the protocol deviations to the analysis will be discussed in Data Evaluation Meeting.

## **3.5        Analysis sets**

### **3.5.1        Enrolled Set**

The Enrolled Set (ES) will consist of subjects who signed an informed consent form in EP0085, enrolling from study EP0083 or from study N01379 or are directly enrolled into EP0085 in Japan. This analysis set is also referred to as "All Subjects Screened".

### **3.5.2        Safety Set**

The Safety Set (SS) will consist of all subjects in the ES who took at least 1 dose of study medication in EP0085. All safety variables will use SS for presentation. In addition,

demographic data, baseline characteristics, medical history, prior and concomitant medications and study drug exposure will use SS for presentation as well.

### **3.5.3 Full Analysis Set**

The Full Analysis Set (FAS) will consist of all subjects in the ES who took at least 1 dose of study medication and have at least 1 seizure record on Daily Record Card (DRC) during the Evaluation Period. All efficacy variables will use FAS for presentation.

## **3.6 Treatment assignment and study groups**

This is an uncontrolled study in which all subjects receive BRV in doses that are optimally adjusted for each subject. It is expected that subjects will receive treatment in accordance with the study design.

Rollover subjects from N01379, EP0083, and directly enrolled subjects need to be analyzed separately. For rollovers from EP0083 a detailed segmentation by randomized drug group in EP0083 is necessary. Unless otherwise specified, results will be presented for each grouping described below:

For tables and figures the study groups will be presented as follows:

- EP0083 Placebo
- EP0083 BRV All
- EP0083 Total
- N01379
- Direct Enrollers
- All Subjects

For subject listings, the study group will be presented as follows:

- EP0083 Placebo
- EP0083 BRV 50mg/day
- EP0083 BRV 200mg/day
- N01379
- Direct Enrollers

For submission purpose, the subgroup tables and figures will be presented by Japan. In Japan subgroup tables and figures, the study groups will be presented in the same manner as overall.

## **3.7 Coding dictionaries**

Medical history and AEs will be coded using the Medical Dictionary for Regulatory Activities (MedDRA) version 18.1. Prior and concomitant medications will be coded using the World Health Organization Drug Dictionary (WHODD) version September 2017. Medical procedures or medical devices will not be coded.

### **3.8 Changes to protocol-defined analyses**

Not applicable.

## **4 STATISTICAL/ANALYTICAL ISSUES**

### **4.1 Handling of missing data**

No rule for handling of missing data will be applied for this LTFU study. Safety and efficacy variables will be analyzed as available. Days with missing information will be ignored in the calculation of the seizure frequency.

Since subjects may drop out from the study at different times, selected summaries will be presented by time interval.

Subjects participating in EP0118 while also enrolled in EP0085 will have missing data for seizure frequency and drug dosing while participating in the EP0118 study. As the duration of the EP0118 study will be short (3-7 days), no imputation for data missing due to participation in EP0118 will be performed. Subjects will be assigned the same dose in EP0118 as that assigned in EP0085 for the two weeks prior to the start of EP0118. As such, time during the EP0118 study will not be subtracted from the exposure calculations (eg, exposure will be from the start of BRV treatment in the EP0085 study until the date of last dose of BRV in EP0085).

For the calculation of variables related to seizure frequency, the dates during participation in EP0118 will be considered as not done for the purpose of efficacy analyses for EP0085 according to the Seizure Count form entry (eg, these dates will not be considered as days evaluated for seizure frequency).

### **4.2 Interim analyses and data monitoring**

No formal interim analysis is planned. However, data will be reported prior to the completion of this study to support regulatory submissions. At a minimum, 2 interim reports are planned after all ongoing subjects have completed Visit 5 (Week 24) and after all ongoing subjects have completed Visit 7 (Week 48). There are no statistical concerns with such interim reports for this open-label LTFU study.

### **4.3 Multicenter studies**

The disposition of subject by study center will present in the summary table by study center. The information of study centers will also be identified in the Subject Disposition listing. Efficacy and safety outcomes will not be assessed for individual study center due to the low expected number for enrollment within each study center.

## **5 STUDY POPULATION CHARACTERISTICS**

### **5.1 Subject disposition**

The number of screen failures and the primary reason for screen failure will be summarized for all subjects screened. The number and percentage of subjects who started, completed and discontinued will be presented by study period, 6-month periods over the Evaluation Period and study group.

The number of subjects by site will be provided in a separate summary table for the ES. The number and percentage of subjects in different analysis sets will be provided based on the ES. The summary of subjects in the SS who discontinued the study due to AE will be presented in a separate table.

All subject disposition related information and subjects who did not meet the inclusion/exclusion criteria will be provided in the subject listings.

## 5.2 Protocol deviations

The number and percentage of subjects with at least one important protocol deviation will be summarized by main category of protocol deviation by study group. The percentage will be based on the Safety Set.

The assignment of subjects to each of the analysis sets will be listed for all subjects enrolled.

## 5.3 Consideration for COVID-19

A new Coronavirus Disease 2019 (COVID-19) CRF to evaluate the impact of global pandemic was created and implemented to collect the information on impacted visit, impact category, and relationship to COVID-19.

The relationship to COVID-19 global pandemic will be assessed and captured as: confirmed COVID-19 infection, suspected COVID-19 infection, general circumstances around COVID-19 without infection or any other deviation from the protocol due to COVID-19.

Summary and listing to describe the impact of COVID-19 will be performed. AE related to COVID-19 vaccination will be flagged in the AE listings (see section 9.2.2.8).

## 5.4 Time to BRV discontinuation

As an additional assessment, the time to BRV discontinuation will be evaluated for both the overall study population and the Japanese subpopulation.

The time to BRV discontinuation will be calculated as follows:

(Date of last dose of BRV – date of first dose of BRV +1) / 30 (in month)

The time to BRV discontinuation will be analyzed using Kaplan-Meier method. The median time, 25% percentile, and 75% percentile of time to BRV discontinuation will be calculated based on SS. Additionally, the cumulative number of events, number at risk, and survival estimate at month 12, 24, 36, 48, 60, 72, 84, and 96 will be provided.

Subjects who discontinued BRV for any reason will be considered as an event. All other subjects will be censored at the date of the last dose of BRV.

In addition to analyzing BRV discontinuation due to any reason, the time to BRV discontinuation will be separately analyzed for the following specific reasons:

- Due to TEAE
- Due to lack of efficacy
- Due to lack of efficacy or TEAE

For each of the BRV discontinuation reason, a summary table will be provided by study group. Additionally, a Kaplan-Meier figure will be provided combining all discontinuation reasons and presented, by study group.

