2.3 Efficacy with BRV in long-term follow-up studies in subjects with partial seizure

Subjects who completed 1 of the primary efficacy studies (N01358, N01252, or N01253) or 1 of the supporting efficacy studies (N01114, N01193, or N01254) had the option to participate in open-label extension studies (N01125, N01199, and N01379) to further evaluate the safety and efficacy of BRV. In the long-term follow-up (LTFU) studies, in which physicians could increase or decrease BRV doses as needed, modal doses of 100mg/day, 150mg/day, and 200mg/day were reported for 22.4%, 46.5%, and 14.7% of subjects with \geq 12 months exposure, respectively. Similar findings were reported for subjects with \geq 24 months exposure.

The long-term follow-up studies indicate a consistently high percentage of subjects continued to receive BRV and clinically relevant efficacy was maintained over time across all regions.

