6.3 Withdrawal criteria

Subjects are free to withdraw from the study at any time, without prejudice to their continued care.

Subjects should be withdrawn from the study if any of the following events occur:

- Withdrawal for safety reasons by the Investigator such as a worsening of the seizure profile, eg, occurrence of status epilepticus, seizure clustering or generalized tonic-clonic seizure, if unknown for the subject

- Subject develops an illness that would interfere with his/her continued participation.
- Subject is noncompliant with the study procedures or medications in the opinion of the Investigator.
- Subject takes prohibited concomitant medications as defined in this protocol.
- Subject or legal guardian withdraws his/her consent.
- There is confirmation of a pregnancy during the study, as evidenced by a positive pregnancy test.
- The sponsor or a regulatory agency requests withdrawal of the subject.
- In the event of a suicide attempt, the subject should be referred immediately to a Mental Healthcare Professional and must be withdrawn from the study.

Subject has active suicidal ideation without specific plan as indicated by a positive response (“Yes”) to Question 4 of the “Since Last Visit” version of the C-SSRS. The subject should be referred immediately to a Mental Healthcare Professional and may be withdrawn from the study based upon the Investigator’s judgment of benefit/risk of continuing the subject in the study/on study medication.

Subject has active suicidal ideation with a specific plan as indicated by a positive response (“Yes”) to Question 5 of the “Since Last Visit” version of the C-SSRS. The subject should be referred immediately to a Mental Healthcare Professional and must be withdrawn from the study.

Investigators should attempt to obtain information on subjects, in the case of withdrawal or discontinuation. The Investigator should make effort (at least 1 phone call and 1 written message to the subject) and document his/her effort (date and summary of the phone call and copy of the written message in the source documents), to complete the final evaluation. All results of these evaluations and observations, together with a narrative description of the reason(s) for removing the subject, must be recorded in the source documents. The eCRF must document the primary reason for withdrawal or discontinuation.

Investigators should contact the Medical Monitor, whenever possible, to discuss the withdrawal of a subject in advance.

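### SAP 5.4 applies Kaplan-Meier to discontinuation by reason without saying how other-reason stops are handled; if they are censored, the curves overstate how many stop for each reason

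*SAP*

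**What the plan says.** SAP 5.4 defines time to discontinuation as days from first to last dose divided by 30, and states: "The time to BRV discontinuation will be analyzed using Kaplan-Meier method". The event is stopping brivaracetam for any reason. The one censoring rule follows: "All other subjects will be censored at the date of the last dose of BRV".

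The section then adds that "the time to BRV discontinuation will be separately analyzed for the following specific reasons": TEAE, lack of efficacy, and either of the two. Each gets a summary table by study group, and all curves go into one Kaplan-Meier figure. The planned outputs are quantiles ("The median time, 25% percentile, and 75% percentile of time to BRV discontinuation will be calculated based on SS") and the "cumulative number of events, number at risk, and survival estimate at month 12, 24, 36, 48, 60, 72, 84, and 96 will be provided".

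No event or censoring rule is written for the three reason-specific analyses. The text in SAP Amendment 4 that introduced the section has the same gap. SAP 4.1 (missing data) does not fill it, and neither document mentions competing events or cumulative incidence.

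Protocol 6.3 shows that other reasons for stopping exist. It lists noncompliance, pregnancy and others, including "Subject or legal guardian withdraws his/her consent". It also requires the reason to be recorded: "The eCRF must document the primary reason for withdrawal or discontinuation".

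**The concern.** The any-reason rules do not transfer to the reason-specific analyses as they stand. Read literally, the event sentence would count every stop as an event in every reason-specific table. The only workable carry-over takes the named reason as the event and censors everyone else at last dose, including subjects who stopped for a different reason.

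That censoring treats someone who withdrew consent as still able to stop later because of a TEAE, which is no longer possible. Their removal shrinks the risk set, so each later reason-specific stop weighs more. Survival falls below the proportion who did not stop for that reason, and any quantile that is reached comes too early.

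Readers are likely to take these tables as showing how many subjects stop for a TEAE or lack of efficacy, and when. Stopping for a TEAE bears on tolerability, which is part of the primary objective.

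**Working it through.** **Planned figure.** The documents give no discontinuation rate or survival figure for SAP 5.4, so there is nothing to reproduce. The direction can be shown exactly. The size needs assumed rates.

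**Direction.** Take 10 subjects. Four stop for other reasons, then one stops for a TEAE, and the rest continue. With the four censored, Kaplan-Meier survival is 1 − 1/6 = 83.3%. The proportion not stopped for a TEAE is 9/10 = 90.0%.

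**Size: inputs**
- A month is 30 days (SAP 3.2.6), so t = months × 30/365.25: 0.986, 3.943 and 7.885 years at months 12, 48 and 96.
- Constant yearly hazards for TEAE / lack of efficacy / other reasons. These are assumptions.

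**Formulas**, with h the TEAE hazard and H the sum of the three:
- Kaplan-Meier complement, other-reason stops censored: 1 − exp(−h·t)
- Cumulative incidence: (h/H)·(1 − exp(−H·t))

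Middle case, month 96: 1 − exp(−0.05 × 7.885) = 32.6%, against (0.05/0.20) × (1 − exp(−0.20 × 7.885)) = 19.8%. As survival, this is 67.4% against 80.2% not stopped for a TEAE.

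TEAE, Kaplan-Meier complement vs cumulative incidence (%):

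| Hazards | Month 12 | Month 48 | Month 96 | All-cause stopping by month 96 |
|---|---|---|---|---|
| 0.01/0.01/0.02 | 1.0 vs 1.0 | 3.9 vs 3.6 | 7.6 vs 6.8 | 27.1 |
| 0.03/0.03/0.03 | 2.9 vs 2.8 | 11.2 vs 10.0 | 21.1 vs 16.9 | 50.8 |
| 0.05/0.08/0.07 | 4.8 vs 4.5 | 17.9 vs 13.6 | 32.6 vs 19.8 | 79.3 |
| 0.08/0.12/0.15 | 7.6 vs 6.7 | 27.1 vs 17.1 | 46.8 vs 21.4 | 93.7 |

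From unrounded values, the gap in the first row is 0.0, 0.2 and 0.8 points. Across the other three rows it is 0.1 to 0.9 points at month 12, 1.2 to 9.9 at month 48 and 4.1 to 25.4 at month 96. The last row is illustrative only, given its 93.7% all-cause stopping.

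**Quantiles, middle case** (years × 365.25/30 = months):
- TEAE 25th percentile: Kaplan-Meier −ln(0.75)/0.05 = 70.1 months. Cumulative incidence approaches 0.05/0.20 = 25.0% only as a limit, so the percentile is not reached.
- Lack-of-efficacy 25th percentile: −ln(0.75)/0.08 = 43.8 months, vs −ln(1 − 0.25/0.40)/0.20 = 59.7 months.
- Median for either reason: ln(2)/0.13 = 64.9 months, vs −ln(1 − 0.50/0.65)/0.20 = 89.3 months.

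**Simulation.** The middle case was run with 217 subjects (the planned total, SAP 2.4), 2000 runs, and administrative censoring assumed uniform over years 2 to 9. For TEAE at month 96 the mean Kaplan-Meier complement was 32.7%, Aalen-Johansen 19.9%, and events divided by n 15.9%, against a true 19.8%. Crude counts therefore err low and Kaplan-Meier errs high.

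**Second set of rates.** Assume 10% stopped for the named reason and 20% for others by month 24. Kaplan-Meier survival vs the proportion not stopped for that reason is 88.8% vs 90.0% at month 24, 78.8% vs 83.0% at month 48 and 62.2% vs 74.7% at month 96. In 2000 simulated trials of 217 with these rates, Kaplan-Meier was lower at month 48 every time.

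**The case against.** **The bias depends on a censoring rule the SAP has not written.** This is true, and the finding is conditional for that reason. But the carry-over is the only workable reading of 5.4 as it stands, and the missing rule is itself a gap.

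**Too low relative to what?** Censoring other reasons gives a recognised net quantity: the chance of stopping for the named reason if no other reason operated. The SAP never says its curves describe the proportion who actually stop. Labelling the curves as net would remove the misreading. However, that interpretation needs the reasons to be independent, which is doubtful for TEAE and lack of efficacy, and the SAP applies no such label.

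**Direct counts exist elsewhere.** SAP 5.1 plans a table of discontinuations due to AE. SAP 9.2.2 and 9.2.2.2 plan the incidence of TEAEs leading to permanent withdrawal. These help for TEAE, but they do not correct for administrative censoring, and no equivalent table is named for lack of efficacy.

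**The large gaps need heavy discontinuation.** Protocol 2.3 reports that "a consistently high percentage of subjects continued to receive BRV" in earlier extension studies. That favours the lowest-rate scenario, where the gap never exceeds 0.8 points at the months shown. The upper-end figures should carry little weight. In the two lower-rate scenarios neither method reaches the TEAE or lack-of-efficacy 25th percentile by month 96, so quantiles come early only where Kaplan-Meier reaches them.

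**Small groups are noisy.** At 17.9%, the binomial standard error √(p(1 − p)/n), ignoring censoring, is about 14.5 points for the 7 planned N01379 subjects and 7.0 for the 30 direct enrollers, against a 4.3-point gap at month 48. For all 217 it is 2.6 points, so the gap matters mainly in the overall tables.

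**Conclusion.** The concern holds and is minor. SAP 5.4 gives no reason-specific event or censoring rule. Under the only workable carry-over, the direction of error is certain: survival is too low, and its complement too high, as a description of who stops for the named reason. The size is uncertain because every hazard above is an assumption. It is negligible at month 12 and with high retention, and it grows with follow-up, so it is largest at the later time points planned to month 96. The any-reason Kaplan-Meier analysis is not affected. No primary conclusion depends on the reason-specific curves, which are descriptive and presented as a supplement.

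**What to change.** Amend SAP 5.4 as follows:
- Keep Kaplan-Meier for discontinuation for any reason.
- For TEAE, lack of efficacy, and either, define the event as stopping for the named reason. Treat stopping for any other reason as a competing event, and report Aalen-Johansen cumulative incidence at months 12 to 96. In the TEAE analysis, a stop for lack of efficacy is a competing event, and vice versa.
- Write the censoring rule for these three: censor only completion, conversion to commercial product, or ongoing treatment at data cut-off, at the date of last dose.
- Keep the planned event counts and numbers at risk.
- Give reason-specific medians and quartiles only where the cumulative incidence reaches them, and otherwise state that they were not reached.
- In the figure, plot the reason-specific curves as cumulative incidence.

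If the sponsor prefers to retain Kaplan-Meier, the minimum is to write the rule and label the curves as net estimates that assume independent reasons.

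The cost is SAP wording and a standard software option. The discontinuation reason and last-dose date are already collected. The small downside is that reason-specific quantiles will often not be reached: under the assumed hazards, TEAE cumulative incidence levels off at h/H, between 22.9% and 33.3%.

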## **6 DEMOGRAPHIC AND OTHER BASELINE CHARACTERISTICS**

All summaries for subject characteristics will be based on SS. Unless otherwise specified, all demographics and other baseline characteristics summaries will be based on data collected in the core study.

### **6.1 Demographics**

Age, age category, gender, racial group, ethnicity, ethnicity subgroup (Japan or China), body weight (kg), height (cm), body mass index (BMI) ( $\text{kg}/\text{m}^2$ ), and BMI category will be summarized by study group for the Safety Set.

The age will be categorized according to the following categories:

- Standard for BRV adult studies:  $<17$ ,  $17$  to  $<65$ , and  $\geq 65$  years
- EudraCT:  $12$  to  $<18$ ,  $18$  to  $<65$ ,  $65$  to  $<85$ , and  $\geq 85$  years
- clinicaltrials.gov:  $\leq 18$ ,  $19$  to  $<65$  and  $\geq 65$  years

The BMI will be categorized according to the following category:

- $<18.5$ ,  $18.5$  to  $<25$ ,  $25$  to  $<30$ ,  $30$  to  $<40$ ,  $\geq 40$

Age will be calculated based on the date of informed consent in EP0085 and date of birth. The result will be kept as integer and the unit of age is years. A birth date of each subject provided from the core studies is imputed to be born on the first day of that month (yyyy-mm-01). Except for age, all other demographic variables will be based on data from baseline of core study.

The demographic variables will be listed by subject.

### **6.2 History of epilepsy**

The following epilepsy-related background variables will be summarized by study group based on the Safety Set:

- Epileptic seizure profile: the number and percentage of subjects experiencing each seizure type at any time based on the Classification of Epileptic Seizures (ILAE,1981) prior to the core study entry will be summarized.
- History of epileptic seizures at the core study: the number and percentage of subjects with a history of status epilepticus and quantitative summaries of epilepsy duration, age at time of first diagnosis of seizure, and percent of life with epilepsy, will be summarized. Percent of life with epilepsy will be calculated as 100 times epilepsy duration relative to the first diagnosis date and divided by the subject's age at the core study entry.

- Classification of epileptic syndrome collected at the core study: the number and percentage of subjects with each epileptic syndrome will be summarized.
- Baseline seizure type and partial seizure frequency collected at the core study: the number and percentage of subjects who experienced each seizure type during the Baseline Period of core study will be presented. Baseline partial seizure frequency will be summarized descriptively for subjects who experienced at least one seizure of type I, IA, IB or IC during the Baseline Period of core study.

For rollover subjects, the data will be obtained from the Baseline Period of N01358 and EP0083. For direct enrollers, the data will be obtained from EP0085 Screening Visit CRF forms.

All above-mentioned baseline characteristics will be listed by subject.

